#### *3.4.2 Secondary Efficacy Endpoints*

Secondary efficacy endpoints include eGFR calculated by CKD-EPI cystatin C equation, CKD-EPI Creatinine equation, CKD-EPI Creatinine-Cystatin C equation and MDRD Creatinine equation. They will be summarized by treatment group over time using descriptive statistics. The analysis of these endpoints may be performed using a mixed-effects model for repeated measures (MMRM) with treatment group, visit, and treatment-by-visit interaction as factors, and baseline value and age as covariates. Point estimates, standard errors, the corresponding 90% confidence intervals and p-values for the differences between treatment groups will be displayed. The treatment comparisons of most interest will be the Least squares (LS) means contrasts of treatment difference at Week 12 and Week 24. In the MMRM model, missing data will not be imputed. For sensitivity analysis, the change in eGFR from baseline may also be analyzed using an analysis of covariance (ANCOVA) model, including treatment group as a factor and baseline value and age

as covariates. Missing data will be imputed by the last observation carried forward (LOCF) method. LS means, standard errors, 90% confidence intervals and p-values for the differences between treatment groups will be displayed. Secondary efficacy endpoints also include the proportion of subjects achieving complete/partial renal remission at Weeks 12 and 24 as defined in section 2.3.2. The proportion will be calculated using the number of subjects in the respective treatment group in the ITT (or PP) population as the denominator. The 90% Clopper-Pearson exact CIs will be estimated for the proportion in each treatment group. The between group comparison will also be carried out using the Newcombe hybrid-score method with a two-sided significance level of 0.10.

Stratified analyses will be conducted for testing difference in proportions between groups. The stratification variables are defined below as used in the randomization stratification. The stratification factor values as collected in the electronic case report forms (eCRFs) will be used for all stratified efficacy analyses, subgroup analyses and summaries of baseline characteristics.

- UPCR <3.5 g protein/g creatinine at baseline versus UPCR  $\geq$ 3.5 g protein/g creatinine at baseline;
- Current use of glucocorticoids/immunosuppressive medications (yes vs. no).

If there is not enough patients in any strata, the stratification variable will be removed from the model.

#### Analysis of Duration of Response

Duration of response analysis will be done only for the responders. The time of duration of response is defined as the time from the initial response of PR or CR to disease progression (not PR or CR). For the subjects without disease progression, the time will be censored at the last clinical assessment. K-M estimate of median time and 90% CI will be provided. If there is not enough responders, this analysis will not be conducted. This analysis may be applied to the responder analyses, such as responders of 30% and 40% reduction of proteinuria.

#### Combining CCX140-B dose groups:

CCX140-B doses groups maybe combined to conduct pooled analysis if the efficacy responses are similar, i.e. all CCX 140 dose groups, and 10 mg and 15 mg BID combined.

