9.4. Sample Size Justification

Assuming the standard deviation (SD) for the change from baseline in the logarithmic transformation of UPCR is 0.70, with 10 subjects per treatment group, the 90% confidence interval (CI) for the between group difference in the log scale will have a $\frac{1}{2}$ width of 0.543. In other words, if the ratio of the treatment over placebo is 0.5 (50% reduction from placebo) in UPCR, the 90% CI will be (0.29, 0.86) (i.e., 14% to 71% reduction).

Assuming SD =8.5 for change from baseline in eGFR, with 10 subjects per group, the 90% CI for the between group difference will have a $\frac{1}{2}$ width of 6.6. If the difference between treatment and placebo is observed to be 10 mL/min/1.73m², the 90% CI will be (3.4, 16.6).

Note the above calculation is based on the SD estimated from Study CL005_140 and an unadjusted 2-sided alpha of 10%.

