## 2.2 Study Design

### 2.2.1 Overview

This study will evaluate the efficacy, safety, tolerability, and pharmacokinetics of up to 12 weeks of treatment with each of three dose regimens of CCX140-B or placebo, when used in combination with stable standard of care therapy in subjects with FSGS with significant proteinuria, assessed as UPCR > 1g/g at Screening.

The target is to enroll 40 adult male or female subjects in this randomized, double-blind, placebo-controlled, Phase 2 study. Subjects will be randomized 1:1:1:1 to one of four treatment groups:

- Group A: Placebo (N=10)
- Group B: CCX140-B 5 mg once daily (N=10)
- Group C: CCX140-B 10 mg twice daily (N=10)
- Group D: CCX140-B 15 mg twice daily (N=10)

[figure not shown]
Subjects will be screened within a period not to exceed 28 days prior to Study Day 1 (the first day of dosing). All subjects will take blinded study medication in the morning and evening, with or without food, for 84 consecutive days. Following the 84-day blinded dosing period, all subjects will take open label CCX140-B for an additional 84 days at the highest dose under evaluation, currently planned to be 15 mg twice daily.

During the treatment period, eligible subjects will visit the study center on Study Days 1, 8, 15, 29 (Week 4), and Weeks 8, 12 (primary endpoint), 13, 16, 20, and 24 for study procedures including interval history, physical examination and vital signs, ECG, study questionnaires, and collection of blood and urine. Subjects will discontinue study drug as of Study Day 169 (Week 24) and will return for a follow up visit on Week 28. When feasible, upon discontinuation of treatment for any reason a sample of whole blood should be collected for assessment of elimination 2, 7 and 14 days after the final dose of CCX140-B (or placebo).

A study schema is depicted in Figure 1. All study procedures are presented in Table 1.

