### 3.1.5 *Hypothesis Testing*

As this is an exploratory study in a rare disease, unless specified otherwise, all statistical tests and confidence intervals will be based on a 2-sided alpha of 0.10. No multiplicity adjustment will be applied to the multiple dose and multiple endpoints comparisons.

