### 3.4.1 Primary Efficacy Endpoint

#### UPCR Change from Baseline

The primary efficacy endpoint (UPCR) will be summarized by treatment group over time using descriptive statistics. Spaghetti plots of UPCR as well as percent change of UPCR (derived from morning void spot urine. If missing 24 hour urine evaluations will be used, if available) from baseline to weeks 4, 8, 12, 13, 16, 20, 24, and week 28 (if available) will be produced by treatment group and for all individual patients for visual inspection. Additionally, percent change of UPCR from week 12 to week 13, 16, 20, 24, and week 28 will be summarized by prior treatment group during the open-label period. The same analyses of for UPCR will be performed at baseline, week 12 and week 24 solely using UPCR values derived from 24-hour urine evaluations (missing assessments will not be replaced with morning void spot urine values).

The primary analysis will use the morning void spot urine results. If baseline or post-baseline morning void spot urine results are not available, 24 hour urine results will be used where available. Please note 24-hour urine assessments at Day 1, Week 12 and Week 24 were added after Protocol Amendment 4.0.

For inferential analysis of the ratio to baseline, UPCR will be loge-transformed to alleviate skewness of the data since data are not normally distributed. A mixed effect model for repeated measures (MMRM) will be performed in the ITT population with treatment, group, visit, and treatment-by-visit interaction as factors and baseline value and age as covariates. Least squares mean differences and the corresponding 90% confidence intervals (CI) between each of the CCX140-B (5, 10, or 15 mg) groups and the placebo group will be back transformed to the original scale. Corresponding P-values will also be presented.

In the MMRM model, missing data will not be imputed. This analysis is unbiased under the missing at random (MAR) assumption. Toeplitz covariance matrix will be used to model within-subject variance-covariance structure for the model errors. If the model does not converge using the Toeplitz covariance matrix, AR(1) covariance matrix will be used. If convergence is still not met, then compound symmetry (CS) will be used.

The code used to generate the MMRM analysis will be similar to the following:

```
*****
Note:
TRT01AN = randomized treatment group (numeric):
    1=Placebo, 2=CCX140-B 5 mg, 3=CCX140-B 10 mg, 3=CCX140-B 15 mg
VISITN = Visit Number

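### The two pooled dose-versus-placebo comparisons are run only if unblinded responses look similar, a term the SAP does not define, so the trial's most precise contrasts may be reported selectively

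*SAP*

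**What the plan says.** The pooling rule is one sentence in SAP 3.4.2, under the heading on combining CCX140-B dose groups: "CCX140-B doses groups maybe combined to conduct pooled analysis if the efficacy responses are similar". The pools are named as "i.e. all CCX 140 dose groups, and 10 mg and 15 mg BID combined". The paragraph gives no numerical meaning for similarity, no endpoint or visit on which to judge it, no decision-maker and no time of decision.

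The primary analysis in SAP 3.4.1 does not depend on this rule. It is an MMRM on log UPCR with treatment, visit and their interaction, and the least squares mean differences "between each of the CCX140-B (5, 10, or 15 mg) groups and the placebo group will be back transformed to the original scale", with 90% intervals and p-values.

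SAP 3.1.5 calls the study exploratory and states that "all statistical tests and confidence intervals will be based on a 2-sided alpha of 0.10" and that "No multiplicity adjustment will be applied to the multiple dose and multiple endpoints comparisons". On the design, SAP 2.2.1 says "Subjects will be randomized 1:1:1:1 to one of four treatment groups", with 10 subjects planned in each.

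The efficacy analysis in Protocol 9.3.5 describes no pooled-dose comparison. SAP section 6 lists only the responder analysis and MCP-MOD as additions to the protocol.

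**The concern.** Efficacy responses by dose group can be compared only after unblinding. A rule that turns on them, with no threshold, lets the analyst see the single-dose results, and in effect the pooled result, before deciding whether the pooled result is formally an analysis of the trial. A favourable pooled estimate can be presented because the doses were similar. An unfavourable one can be left out because they were not. A reader of the report could not tell which had happened.

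Elsewhere the SAP closes this kind of gap. Per-protocol exclusions (3.2.3) and the handling of major deviations (3.3.2) are to be documented before unblinding, and the review of non-allowed medications for the responder analysis (3.4.1) comes before database lock. The pooling paragraph has no such safeguard.

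What is at stake is precision. With 10 subjects per arm, a single-dose comparison is wide, and the pooled contrasts are the sharpest available answer to whether CCX140-B lowers UPCR relative to placebo.

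**Working it through.** **Inputs.** SD 0.70 for log UPCR and 8.5 for eGFR (Protocol 9.4: "Assuming the standard deviation (SD) for the change from baseline in the logarithmic transformation of UPCR is 0.70"; "Assuming SD =8.5 for change from baseline in eGFR, with 10 subjects per group"); 10 per arm, four arms; 90% two-sided intervals.

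**1. The plan's own figure.** Half-width = t(0.95, n1+n0−2) × SD × √(1/n1 + 1/n0).
- Log UPCR: 1.734 × 0.70 × √(1/10 + 1/10) = 0.543. At a ratio of 0.5 the interval is 0.5·exp(±0.543) = 0.29 to 0.86.
- eGFR: 1.734 × 8.5 × 0.447 = 6.6.

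Both match the documents. They match only if 0.70 is the SD of one subject's change, as the protocol words it. SAP 2.2.4 calls it the SD of the group difference, which would not give 0.543.

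**2. The pooled contrasts on common degrees of freedom.** With one variance estimated from all four arms, df = 40 − 4 = 36 and t = 1.688.

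| Contrast with placebo | n1 v n0 | √(1/n1+1/n0) | Half-width (log UPCR) | 90% CI at ratio 0.5 |
|---|---|---|---|---|
| One dose | 10 v 10 | 0.447 | 0.529 | 0.29 to 0.85 |
| 10+15 mg twice daily | 20 v 10 | 0.387 | 0.458 | 0.32 to 0.79 |
| All doses | 30 v 10 | 0.365 | 0.432 | 0.32 to 0.77 |

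The relative gains are 1 − 0.387/0.447 = 13% and 1 − 0.365/0.447 = 18%. They depend only on group sizes, so they hold for any SD; for eGFR the half-widths are 6.4, 5.6 and 5.2. Comparing 0.432 with the documents' 0.543 would suggest 20%, but that mixes 36 with 18 degrees of freedom.

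If the true ratio were 0.5 in every pooled dose, power (t-based, each comparison on its own n1+n0−2 df) would be about 69% for one dose, 80% for 10+15 mg and 85% for all doses.

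**3. How much hangs on the undefined word.** The SAP gives no threshold, so these readings are assumptions. In 400,000 simulated trials with three truly equal doses, the active arms would be called similar in:
- about 90% of trials if the test is an F-test among active arms with p > 0.10;
- about 60% if the active geometric means must lie within a factor of 1.5;
- about 24% if they must lie within a factor of 1.25.

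With a real dose response (ratios to placebo of about 0.90, 0.70 and 0.50), the F-test reading would still call the doses similar in about 52% of trials.

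**4. Error rates with no true effect, two-sided 0.10, same simulation settings.**
- 10+15 mg pooled contrast, given that the two doses look similar: about 10%.
- 10 mg and 15 mg each tested against placebo, no pooling: about 17% for at least one false claim.
- Three single-dose contrasts: about 23%.
- Those three, with the 10+15 mg pool added only if similar: about 24%.
- All five contrasts always reported: about 24%.

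**The case against.** The case on the other side is substantial. The study is declared exploratory and multiplicity is openly left unadjusted. The primary contrasts are fixed. Pooling is an optional paragraph within the secondary endpoints section, and the make-up of both pools is stated in advance. MCP-MOD already uses all four arms whether or not the doses look similar. The arms run from 5 mg to 30 mg per day in a dose-ranging design, so an average over them need not be the quantity of most interest.

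Most of this stands and limits the point. A reader might infer that conditional pooling inflates the false-positive rate. The figures in step 4 do not support that. The pooled test keeps its 10% level given similarity, and unadjusted separate tests of 10 mg and 15 mg already reach about 17% with no pooling choice at all. A reader might also infer that pooled results could replace the single-dose results. SAP 3.4.1 produces the single-dose contrasts unconditionally, and the pooling paragraph does not suspend them.

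Three parts of the objection do not answer the concern. Exploratory status waives adjustment, not advance specification; where nothing is adjusted, a fixed and fully reported set of comparisons is the reader's main protection. MCP-MOD tests for a dose response and does not estimate a pooled difference from placebo. The similarity condition is also a weak guard against averaging unlike doses, since under one reasonable reading it passes about half of trials with a real dose response.

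**Conclusion.** The concern holds as a matter of selective reporting and forgone precision. The two pooled comparisons can be run or omitted according to unblinded results under an undefined criterion, although they are 13% and 18% narrower than a single-dose contrast. The percentages assume the planned 10 per arm and a common variance. The half-widths themselves also assume SD 0.70 and 36 degrees of freedom, and the fitted MMRM will shift them somewhat through covariates, repeated measures and dropout.

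The documents do not support going further. The primary analysis is not compromised, the choice of pool is not open-ended, and the rule is not a material source of extra false claims. The overall rate is about 24% whether the 10+15 mg pool is conditional or both pools are fixed.

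**What to change.** Delete the similarity condition. Pre-specify two further Week 12 contrasts in the primary MMRM: the equally weighted mean of all three CCX140-B groups versus placebo, and the equally weighted mean of the 10 mg and 15 mg twice-daily groups versus placebo. Report both, whatever they show, beside the three single-dose contrasts, and label them as supportive average effects across doses. Add the pooled contrasts to SAP section 6.

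The cost is two contrast statements in a model already planned, with no new data. The numeric treatment codes in the SAP 3.4.1 program note need correcting first, because 10 mg and 15 mg are both shown as code 3. If the doses differ in effect, the pooled estimate is harder to interpret, which is the reason for the label. The change makes every comparison visible; it does not control the error rate across the five.

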#### Proteinuria changes based on 24 our urine collection (see also section 3.4.1):

Proteinuria analyses of UPCR and UACR described above that were derived from spot urine will be repeated for 24-hour urine analyses if available.

### 3.4.3 Exploratory Efficacy Endpoints

The exploratory endpoints in section 2.3.3 will be summarized by treatment group over time using descriptive statistics, including MCP-1 levels by treatment group.

An exploratory analysis of UPCR using the same MMRM analysis method as described in Section 3.4.1 will be carried out with the addition of baseline urinary MCP-1 to creatinine ratio and baseline plasma MCP-1 as covariates.

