9.3.5. Efficacy Analyses

Summary statistics will be calculated for each of the efficacy parameters. For categorical endpoints, number and percentages will be calculated. For continuous variables, numbers, means, medians, ranges and standard deviations will be calculated. Point estimates and

corresponding 90% confidence intervals will be estimated for the difference between CCX140-B and placebo groups.

Data that are not normally distributed, e.g., UPCR, will be log-transformed before analysis.

Point estimates and corresponding 90% confidence intervals will be estimated for the difference between CCX140-B and placebo groups.

Because of the relatively small size of the study, inferential statistical analyses may not be appropriate. Where possible, change from baseline to Day 85 and from Day 85 to Day 169 in UPCR will be analyzed using the mixed-effects model for repeated measures (MMRM), with treatment group, visit, and treatment-by-visit as factors and baseline UPCR and age as covariates. The between group comparison will be computed using the simple contrast from the model. Analysis of covariance (ANCOVA) with last observation carried forward (LOCF) for missing data will also be used for sensitivity analysis. The MMRM and ANCOVA analyses will also be applied to the eGFR endpoint.

Proportion of subjects achieving partial response will be calculated for each treatment group. The between group comparison will be carried out using the Fisher's exact test.

The exploratory endpoints will be analyzed using MMRM model or ANCOVA as described for the primary efficacy endpoint analysis.

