### 2.3.3 Exploratory Endpoints

Exploratory endpoints include:

- Change from baseline of proteinuria in subjects treated with CCX140-B versus placebo over time
- Change from baseline (absolute and percent change) in urinary albumin:creatinine ratio (UACR). The response rate across dose groups for patients achieving 30% reduction in

UACR from baseline at Week 12 will be calculated, with the number of subjects in the respective treatment group in the ITT (or PP) population being the denominator. The analysis will be repeated for reductions of 20%, 40% and 50%.

- Change from baseline in urinary MCP-1:creatinine ratio
- Change from baseline in blood monocytes (absolute and %), T, B and NK cells
- Change from baseline in Health-related Quality of Life changes based on Short Form 36 version 2 (SF-36 v2) and EuroQuality of Life-5 Domains-5 Levels (EQ-5D-5L) questionnaires
- Change from baseline in serum albumin
- Relationship among PK, eGFR, serum albumin and UPCR

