## **6 CHANGES FROM PROTOCOL-SPECIFIED STATISTICAL ANALYSES**

Per ChemoCentryx's request, responder analysis and MCP-MOD have been added for the analysis of the primary efficacy endpoint.

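### The SAP gives UACR no between-arm model, ratio to placebo or 90% CI, although the protocol promised MMRM or ANCOVA for exploratory endpoints, and SAP section 6 does not list the change

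*SAP*

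**What the plan says.** **Protocol.** Section 9.2.3 lists change from baseline in UACR as an exploratory efficacy endpoint. Section 9.3.5 gives the method: "The exploratory endpoints will be analyzed using MMRM model or ANCOVA as described for the primary efficacy endpoint analysis". The same section promises point estimates and 90% CIs for CCX140-B against placebo. It also warns that formal inference may be unsuitable in so small a study. Section 9 calls for geometric means where a variable needs a log transformation.

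**SAP.** Section 1 states that the SAP overrides the protocol's analyses. Section 2.3.3 keeps UACR as an absolute and a percent change and adds responder summaries: "The response rate across dose groups for patients achieving 30% reduction in" UACR at Week 12, then "The analysis will be repeated for reductions of 20%, 40% and 50" per cent. Section 3.4.3 gives the method for all of these endpoints: "The exploratory endpoints in section 2.3.3 will be summarized by treatment group over time using descriptive statistics". The only model in 3.4.3 is a UPCR MMRM with added MCP-1 covariates. A short paragraph on 24-hour urine at the end of 3.4.2 says the UPCR and UACR analyses set out before it will be repeated on 24-hour samples.

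**Declared changes.** SAP section 6 reports only that "responder analysis and MCP-MOD have been added for the analysis of the primary efficacy endpoint".

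**The concern.** The protocol promised a model-based comparison of UACR between arms, and the superseding document has none. It also does not say that the comparison was dropped.

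UACR is the measure on which the earlier diabetic nephropathy study is summarised in protocol 2.4.1, as mean percent change by arm with CIs. If the SAP is followed as written, the study report will show UACR summaries by arm and four overlapping response rates per arm. It will have no adjusted UACR ratio to placebo, with an interval, to set beside that earlier evidence. With 10 subjects in an arm, one subject crossing a cut moves a response rate by 1/10, or 10 percentage points.

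The same gap affects the other endpoints of SAP 2.3.3, including urinary MCP-1:creatinine and serum albumin.

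**Working it through.** **1. Is a UACR contrast written anywhere in the SAP?**

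| Place in SAP | What it gives UACR | Between-arm estimate or CI? |
|---|---|---|
| 2.3.3 | absolute and percent change; response rates per arm at 20, 30, 40 and 50% | no |
| 3.1.4 | default summaries, without geometric means | no |
| 3.4.1, MMRM and responder analyses | written for UPCR only | not for UACR |
| 3.4.2, remission | Newcombe comparison of remission proportions | not for UACR |
| 3.4.2, 24-hour urine paragraph | repeats the UACR analyses already described, which are those of 2.3.3 | no |
| 3.4.3 | descriptive statistics | no |
| 3.5.3 | exploratory relation of PK to UACR, in a separate report | not a comparison of arms |
| 6 | silent on this change | – |

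The answer is no.

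**2. Reproduce the plan's own precision figure.** The inputs are:
- "with 10 subjects per treatment group" (protocol 9.4)
- "Subjects will be randomized 1:1:1:1 to one of four treatment groups" (SAP 2.2.1), so each contrast is 10 v 10
- "all statistical tests and confidence intervals will be based on a 2-sided alpha of 0.10" (SAP 3.1.5)
- SD 0.70 for the change in log UPCR and a ratio of 0.5 (protocol 9.4)

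Half-width = t(0.95, 18 df) × SD × √(2/n) = 1.734 × 0.70 × √0.2 = 0.543, as stated. The CI is 0.5 × exp(±0.543) = (0.29, 0.86), also as stated. SAP 2.2.4 labels 0.70 as the SD of the group difference, but only the protocol's within-group reading gives 0.543.

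**3. Illustration for UACR.** The documents give no SD or target effect for UACR, so the UPCR values are borrowed. Further assumptions are log-normal change and a placebo mean change of zero.

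- *Log scale.* The standardised difference is ln(2)/0.70 = 0.693/0.70 = 0.99. The two-sample noncentral t with 18 df gives power of 68.6%.
- *Response at a cut c.* The placebo rate is Φ(ln(1−c)/0.70). The active rate is Φ((ln(1−c) − ln 0.5)/0.70). All 11 × 11 outcomes are enumerated, counting those where an unstratified 90% Newcombe interval excludes zero.

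| Cut | Placebo rate | Active rate | Newcombe power | Loss from 68.6% |
|---|---|---|---|---|
| 20% | 37.5% | 74.9% | 56.0% | 12.6 points |
| 30% | 30.5% | 68.5% | 56.9% | 11.7 points |
| 40% | 23.3% | 60.3% | 55.3% | 13.3 points |
| 50% | 16.1% | 50.0% | 50.6% | 18.0 points |

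**4. Range.**
- *SD.* At the 30% cut and ratio 0.5, SD 0.5 to 0.8 gives a loss of 10 to 12 points.
- *Effect.* At SD 0.70, a ratio of 0.6 loses 8 to 15 points over the four cuts, and 0.7 loses 4 to 10.
- *Earlier study.* The overall UACR result in protocol 2.4.1 is −18% on 5 mg against −2% on placebo, a ratio of 0.82/0.98 ≈ 0.84. At that ratio and SD 0.70, log-scale power is 14.8% and the loss is 0 to 4 points.

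**The case against.** **The study is small, UACR is exploratory, and the protocol lets the SAP override it.** All true. UPCR, the primary proteinuria endpoint, keeps its log-scale MMRM with 90% CIs, which limits the consequence. But size does not explain treating UACR differently: SAP 3.4.1 and 3.4.2 plan intervals and p-values for UPCR and, optionally, for eGFR in the same arms of 10. A ratio with an interval is estimation, which protocol 9.3.5 promised as well. Authority to change a method also does not excuse leaving the change out of section 6.

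**The 24-hour urine paragraph points back to section 3.4.1, so a UACR model may have been intended.** That is possible. However, no UACR model has been described by that point, so the paragraph leaves doubt about intent without supplying a method.

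**A reader might infer that the cuts replace the continuous analysis, at a cost of 12 to 31 points of power.** The documents do not support this.
- SAP 2.3.3 keeps continuous UACR change. What replaces the model is a descriptive summary, with the response rates added.
- The SAP assigns no test to UACR response. Its Newcombe comparisons are for UPCR response and remission.
- The 31 comes from Fisher's exact test at the 30% cut (38.0% power). The protocol names that test only for partial response, and the SAP uses Newcombe there. At 10 v 10 its true size is about 4% against a nominal 10%, so much of that loss is the test's conservatism.

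**Conclusion.** The point holds as an undisclosed departure from the protocol. For UACR, and for the other exploratory endpoints of SAP 2.3.3, the promised MMRM or ANCOVA has become descriptive statistics by arm. No UACR ratio to placebo or 90% CI is specified. This rests on the text alone and needs no assumption.

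The consequence is modest, because the primary proteinuria endpoint is still modelled on its full scale. What is lost is an adjusted UACR estimate comparable with the earlier study.

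The power figures are a scenario. With the UPCR values of SD 0.70 and ratio 0.5, comparing response rates by Newcombe interval would give 51 to 57% over the four cuts against 68.6% on the log scale, a loss of 12 to 18 points. At ratio 0.84 the loss is 0 to 4 points. These figures show why the response rates would be a weak substitute if a large effect existed. They do not measure a loss built into the plan.

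**What to change.** 1. In SAP 3.4.3, state that log UACR, as a ratio to baseline, will be analysed with the section 3.4.1 MMRM (or ANCOVA), adjusting for log baseline UACR and age. Report Week 12 geometric mean ratios to placebo with 90% CIs, and label the 20, 30, 40 and 50% response rates as supportive.
2. Apply the same model to log urinary MCP-1:creatinine and, untransformed, to serum albumin.
3. Make the 24-hour urine paragraph in 3.4.2 refer to this model explicitly.
4. In section 6, list and justify any exploratory endpoint that stays descriptive only.

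The cost is a few sentences and further runs of existing MMRM code. UACR is already collected at every scheduled study visit. The downside is a few more exploratory estimates, unadjusted for multiplicity, to report.
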